### **11.5 Monitoring Investigations**

Monitoring visits to the principal investigator's site will be made periodically during the study, to ensure that the clinical trial is being conducted in strict accordance with the protocol, in compliance with Good Clinical Practice as defined by the FDA and by Harmonized Tripartite Guidelines, and that the clinical data can be validated against source documentation at the investigative site. Original source documents will be reviewed for verification of data recorded on the CRFs and/or in the electronic database. The investigator guarantees direct access to original source documents by the FDA, their designees, and appropriate regulatory authorities. In the event that the original medical record cannot be obtained for a patient that is seen by a non-study physician at a non-study institution, photocopies or fax documentation of the original source documents must be made available for review.

### **11.6 Source Documentation**

Investigators are responsible for maintaining information in the study patients' medical records and/or paper source documents that are kept in the subject study binder that corroborate data entered into the CRF. The following documents will be maintained and made available as required by the investigators, designated monitors and/or regulatory inspectors:

1. Medical and surgical history/physical condition of the patient prior to participation in the study in order to verify protocol entry criteria.
2. Dated and signed notes in the patients' medical record and/or subject study binder that verify that informed consent was obtained.
3. Dated and signed notes from each patient visit.
4. Description of device implantation procedure (date, time, medications, etc)
5. Dated printouts of diagnostic reports of assessments (CT, etc)
6. Adverse event reporting and follow-up of the AE.
7. Patient's condition upon completion of or withdrawal from the study.

### **11.7 Maintaining Records**

The investigator will maintain hard or electronic copies of correspondence, data, devices, adverse device effects, and other records related to the clinical trial for at least two (2) years after study completion.

It is the responsibility of the investigator and the study staff to maintain a comprehensive and centralized filing system of all relevant study documentation which may include:

- Patient Files - which substantiate the data entered in the electronic and/ or paper Case Report Forms for all required tests and procedures.
- Patient Identification Log - a list correlating all patient names, appropriate identifying information, etc., to the investigator - assigned patient number.
- Screening Log - which should reflect the reason any patient was screened for the study and found to be ineligible.
- Monitoring Visit Log - which lists dates of monitor visits.
- IRB Correspondence - includes approval letter(s), and any adverse event reporting or other correspondence with the IRB.
- Site Correspondence - letters or fax sent to the FDA from the investigator or study coordinator.
- Signed Informed Consent for each patient
- Device log-acknowledging receipt and return, if necessary, of the t-Branched or CMD devices.

In compliance with current regulatory guidelines regarding the monitoring of clinical studies, it is requested that the investigator permit the study monitor to review and duplicate information, in a de-identified format, in the patient's medical record that is directly related to the study. This information may include relevant study documentation, including the patient's medical history, to verify eligibility, laboratory test results to verify transcription accuracy, x-ray reports, admission and discharge summaries for hospital or outpatient admissions occurring while the patient is participating in the study, and autopsy reports for deaths occurring during the study (if available).

As part of the required content of informed consent, the patient must be informed that his/her medical record will be reviewed and, possibly, duplicated by monitor or government regulatory authorities. Should access to the medical record require a separate waiver or authorization, it is the investigator's responsibility to obtain such permission from the patient in writing before the patient is entered into the study.

### **11.8 Study Deviations**

A study deviation is defined as an event where the investigator did not conduct the study according to the investigational plan or protocol. The deviation event will be collected on the **Master Deviation Log**. The investigator is responsible for reporting deviations in accordance with the reviewing IRB policies.

FDA regulations require that investigators maintain accurate, complete, and current records, including documents showing the dates of and reasons for each deviation from the protocol. The following information outlines requirements for the reporting of protocol deviations:

Type of Deviation	Investigator to notify:	Reporting timeline
Emergency procedures to protect the life or physical well-being of a patient	Reviewing IRB and FDA	Within 5 business days of event
Changes in or Deviations from the investigational plan	Prior approval from: IRB and FDA	Prior to use
Non-urgent protocol deviation	IRB (if required)	Deviations directly related to the study endpoints will be summarized and submitted in an annual report to the FDA

### 11.9 Termination of Study

The FDA retains the right to terminate the study at any time. Specific instances, which may precipitate study termination, are:

- Unsatisfactory patient enrollment with regard to quality and quantity.
- Deviations from protocol, without prior approval from the FDA.
- Inaccurate, incomplete, and/or untimely data recording on a recurrent basis.
- The incidence and/or severity of adverse experiences in this or other studies indicating a potential health hazard caused by the device.
- Submission of fraudulent data.

## 12.0 STUDY COMMITTEES

### 12.1 Data Safety Monitoring Plan

A Data Safety Monitor (DSM) will review the progress of the clinical study. The monitor will be responsible for reviewing the data associated with the device and the patients. The monitor will provide independent recommendations to the investigator based on his review of the data. The monitor will meet with the Clinical Events Committee annually, at a minimum. [name] will serve as the DSM. [name] has extensive experience in the clinical care of patients with TAAA both in the operating room and in the intensive care unit.

### 12.2 Clinical Events Committee

The Clinical Events Committee (CEC) will be used to review and adjudicate all device related adverse events and all serious adverse events regardless of the relatedness to the device. The

CEC shall also determine which adverse events (other than those listed in Section 9.1.1) are considered Major Adverse Events for evaluation of the primary and secondary safety endpoints. The committee shall consist of at least three (3) physicians representing multiple specialties familiar with thoraco-abdominal aortic aneurysm repair. The CEC will be comprised of Drs., [name], [name], [name] and [name]. [name] is a Professor of Surgery and Director of Surgical Critical Care at Harborview Medical Center. [name], is an Acting Instructor in the Department of Medicine and a member of the Medicine Consult Service at University of Washington Medical Center and the Seattle Cancer Care Alliance. [name] is a Clinical Professor with the Department of Pain and Anesthesia.. [name] PhD is an Associate Professor of Anesthesiology with expertise in the study of quality and safety. The CEC will provide their review to the DSM and will meet annually at a minimum.

### **13.0 INFORMED CONSENT**

All patients or designated patient representatives must provide written informed consent in order to join the Study Group, in accordance with the reviewing IRB policy and procedures. The process of obtaining informed consent must be documented in the patient's medical record and/or Subject Study Binder. If changes to the investigator's informed consent template are to be made, these changes must be approved by the local IRB. A template for the Informed Consent is provided in **Appendix V: Informed Consent Template**.

## **APPENDIX III: ASA CLASSIFICATION SYSTEM**

### **American Society of Anesthesiologists Classification System**

The American Society of Anesthesiologists (ASA) presents a graded scale assessing a patient's risk of undergoing anesthesia. The scale represents the significance of the patient's underlying illnesses prior to anesthesia. The following provides a description of the four grades of the ASA scale:

#### **ASA I**

Healthy individual *without any systemic disease*, undergoing elective surgery. Patient not at extremes of age. (*Note: Age is sometimes ignored as affecting operative risk; however, patients at either extreme of age are thought to represent increased risk.*) Some examples are a fit man with an inguinal hernia, and a fibroid uterus in an otherwise healthy woman.

#### **ASA II**

Individual *with one system, well-controlled disease*. Disease does not affect daily activities. Other anesthetic risk factors, including mild obesity, alcoholism, and smoking can be incorporated here. Examples include non-limiting or only slightly limiting organic heart disease, essential hypertension, anemia, or mild diabetes.

#### **ASA III**

Individual *with multiple system disease or well controlled major system disease*. Disease does limit daily activities. No immediate danger of death from any individual disease. Examples include severe organic heart disease, severe diabetes with vascular complications, moderate to severe degrees of pulmonary insufficiency, angina or healed myocardial infarction.

#### **ASA IV**

Individual in imminent danger of death. Surgery is viewed to be last resort at salvaging life. Individual not expected to live through the next 24 hours. In some cases, the individual may be healthy prior to catastrophic event that led to the current medical condition. Examples include ruptured abdominal aortic aneurysm with profound shock; major cerebral trauma with rapidly increasing intracranial pressure; massive pulmonary embolus.

## APPENDIX IV: SCHEDULE OF ACTIVITIES

Procedure	Baseline	Treatment	Discharge	1 Month Follow-Up	6 Month Follow-Up 	12 Month Follow-Up	Annual Follow-Up
Medical/Surgical History	X 						
Physical Exam	X 		X	X	X	X	X
Spiral Contrast Enhanced CT	X 			X 	X 	X 	X 
Laboratory Assessment (creatinine, PT, PTT, INR, CBC)	X 		X 	X 	X 	X 	X 
Adverse Event Assessment		X	X	X	X	X	X
Concomitant Medication Assessment (anticoagulants, antiplatelets, antibiotics, ACE inhibitors, Beta blockers and statins only)	X		X	X	X	X	X
Device/aneurysm assessment based on imaging (endoleak, migration, integrity, patency)				X	X	X	X

 CBC, PT, PTT and INR are optional after Baseline.

 Baseline med/surgical history, physician exam performed no more than 3 months prior to the implant/surgical procedure.

 Laboratory assessments performed no more than 3 months prior to surgical/implant procedure

 Serum pregnancy HCG test for females of childbearing potential performed no more than one week prior to surgical/implant procedure

 Baseline contrast enhanced CT must be obtained within 4 months of anticipated treatment date.

 If subject not able to tolerate contrast enhanced CT, a non contrast CT and visceral branch duplex ultrasound can be performed

 Subjects who undergo TEVAR only will not have the 6 month visit

## APPENDIX VI: CT SCANNING TECHNIQUES

### Reminders:

- This study requires contrast enhanced Spiral CT data for reconstruction.
  - Data must be uncompressed DICOM
  - Patient motion should be avoided during scan. If possible, avoid scanning non-patient objects in field of view. Do not change patient position, table height, or field of view during scan. If patient moves, repeat the study in its entirety.

	Minimum Protocol (Required)	High Resolution Protocol (Recommended)
Scan Mode	Helical	Helical
Scan Parameters	100-140kVp, Auto mAs or 170-400 mA scan time of 0.5sec	100-140kVp, Auto mAs or 170-400 mA scan time of 0.5sec
Slice Thickness	3mm	0.625 – 2.5mm
Slice Interval	3mm	0.625 – 2.5mm
Pitch	0.984:1	0.984:1
Superior Extent TAAA	Lung apices	Lung apices
Inferior Extent TAAA	Pre-op: Lesser trochanter of femurs to include femoral bifurcations  Post-op: At least 2cm distal to the lowest hypogastric artery origin	Pre-op: Lesser trochanter of femurs to include femoral bifurcations  Post-op: At least 2cm distal to the lowest hypogastric artery origin
Contrast	Standard per Radiology Department	Standard per Radiology Department
Volume	80 – 150 ml contrast with 40ml saline flush or Standard Contrast Volume with Saline Flush per Radiology Department	80 - 150ml contrast with 40ml saline flush or Standard Contrast Volume with Saline Flush per Radiology Department
Rate	4 - 6 ml/sec	4- 6 ml/sec
Scan Delay	ROI – threshold 70-100 HU in aorta	ROI – threshold 70-100 HU in aorta
Field of View	Large Body	Large Body
Reconstruction Algorithm	Standard	Standard

## APPENDIX VII: EXPLANT PROCEDURE

Explant reports will be included in a progress report to the FDA with an Explant CRF.

**Explant During Surgical Conversion:** The objective of device removal is to minimize trauma or damage to the device at the time of surgical excision from the patient, while maintaining the patient's safety. It is also important to minimize surrounding tissue disturbance so that a thorough pathological evaluation can be made.

1. If possible, a swab should be used to obtain material for microbial culture prior to removal of the explant.
2. Attempt to identify all components including their orientation so that they may be maintained in the same relative position as they were *in situ*.
3. Attempt to remove the specimen en bloc from superior to the proximal stent to inferior to the distal stent.
4. The residual blood should be rinsed from the explant surfaces utilizing physiological solutions such as Ringer's lactate or normal saline avoiding disturbance to the inside surface of the explant.
5. All samples should be fixed in 10% neutral buffered formalin.
6. Explant case report forms should be completed at this time
7. An operative report and a separate report from the examining pathologist should be sent to the FDA, if available.

**Explant During Autopsy:** The objective of device removal is to excise en bloc from superior to the proximal stent to inferior to the distal stent. The abdominal aorta and iliacs should not be opened nor should any endovascular device manipulation be done. Photos should be taken, if possible, in anterior-posterior as well as oblique and lateral views. The external characteristics and the relationship to surrounding viscera should be noted based on the guidelines on the case report forms. Adhesions to viscera as well as evidence of fistula formation by erosion of the endograft through the arterial wall should be noted. Any problems or abnormalities of this type should be photographed *in situ*, if possible.

1. If possible, a spiral CT scan with 3-D reconstruction should be obtained of the endograft prior to explantation of the device. Spiral CT should be performed before immersion of the specimen in fixative.
2. Attempt to identify all components including their orientation so that they may be maintained in the same relative position as they were *in situ*.
3. Attempt to remove the specimen en bloc from superior to the proximal stent to inferior to the distal stent.
4. All samples should be fixed in 10% neutral buffered formalin.
5. An autopsy report and a separate report from the examining pathologist should be sent to the FDA, if available.

\*These guidelines have been furnished by the Lifeline Registry of Endovascular Aneurysm Repair.

## 1.0 TRIAL SAFETY

### 1.1 Potential Risks and Benefits for Participants

#### Potential Risks:

The risks associated with the use of this study device are not currently known. Although the adverse events associated with the use of physician modified endovascular grafts may be less than for standard open surgical repair, inherent risks exist, as with many medical procedures. However, risks that have been associated with repair of TAAAs with this type of device include, but may not be limited to:

- Cardiac events such as congestive heart failure (CHF), volume overload, arrhythmias, myocardial infarction (MI), chest discomfort or angina, elevations in creatinine phosphokinase (CPK), hypotension
- Pulmonary events such as pulmonary insufficiency, pneumonia, respiratory depression or failure, pulmonary edema, pulmonary embolism
- Cerebral events such as cerebrovascular accident (hemorrhagic or embolic), reversible ischemic neurologic deficit, transient ischemic attacks (TIA)
- Acute and chronic renal insufficiency or failure, renal microembolism, dialysis
- Operative and post-operative bleeding disorders, hemorrhage and coagulopathy
- Insertion and other vascular access site complications such as infection, bleeding, delayed healing, hematoma, dehiscence, seroma, nerve injury/damage, neuropathy, neuralgia, vasovagal response
- Vascular injury including damage to blood vessels and surrounding tissues, vessel dissection, perforation, plaque dissection, collateral vessel occlusion, tissue loss, arterial fistula, limb loss, gangrenous disease, worsened or new onset claudication, edema
- Neurological complications, such as paralysis (temporary or permanent), paraplegia, monoplegia, paresis, spinal cord ischemia, hemiplegia, bowel or bladder incontinence
- Multi-system organ failure
- Embolic and thrombotic events such as deep vein thrombosis, thromboembolism, microembolism, thrombophlebitis, phlebothrombosis, pulmonary embolism, air embolism
- Gastrointestinal events such as paralytic or adynamic ileus, obstruction, fistulas, and Intestinal ischemia due to visceral artery injury, branch failure, or embolization
- Impotence, erectile dysfunction
- Urinary events such as hematuria, urinary retention, and urinary tract infection
- Radiation injury, late malignancy
- Allergic reaction to x-ray dye such as flushing, nausea, vomiting, itching, hives
- Generalized inflammatory response that may be associated with elevated levels of systemic mediators of inflammation, elevated temperature
- General discomfort related to the procedure or tests, sore throat, pain

- Infection—urinary tract, systemic or localized, sepsis, endograft
- Device events such as endograft occlusion, migration, dislodgement, endoleak, and/or stent fracture
- Branch vessel occlusion, narrowing or fracture
- Aneurysm rupture
- Conversion to open surgical repair
- Death
- Patients who have the first stage TEVAR repair and do not go on to have the second B-TEVAR stage will remain at risk of aneurysm rupture.

Potential Benefits:

Potential benefits of physician modified endovascular grafts compared to open surgical aneurysm repair may include, but are not limited to:

- Freedom from open surgery;
- Freedom from general anesthesia and/or the ability to use other forms of anesthesia that do not require mechanical ventilation;
- Reduction of complications; and
- Reduction in hospitalization and recovery time.

**1.2 Adverse Event and Serious Adverse Event Collection and Reporting**

An adverse event (AE) is any new, undesirable medical occurrence or change (worsening) of a pre-existing condition that occurs in a patient, whether or not considered to be associated with the product. Elective hospitalizations for pre-existing conditions (e.g., elective cosmetic procedures) are not adverse events. Requirements for reporting AEs are dependent upon the reviewing IRB policy. Adverse events will be reviewed by a Clinical Events Committee (CEC). The CEC will meet periodically, a minimum of annually. Adverse Event information is recorded in the **Adverse Event Case Report Form (CRF)**.

For purposes of this study, the following events are not considered adverse events, because they are expected to occur in conjunction with the index procedure or are associated with customary, standard care of patients undergoing endovascular AAA repair procedures:

- Early post-operative pain (within 72 hours of index procedure) at the access site and/or related to position on procedure table (i.e. low back pain)
- Post-anesthesia/conscious sedation emesis, nausea, or headache (within -72 hours of index procedure)
- Electrolyte imbalance without clinical sequelae following index procedure, even if requiring correction
- Low grade temperature increase (< 100.5 °F)
- Blood loss not requiring transfusion and not resulting in decreased hematocrit.

- Minor, localized tenderness, swelling, induration, bruising, erythema, hematoma etc. at vascular access site that does not require surgical intervention, evacuation, transfusion, or antibiotics
- Non-sustained arrhythmia not requiring treatment or intervention
- Prophylactic administration of atropine
- Prophylactic pacing
- Isolated, non-sustained PVCs/PACs
- Asymptomatic hypotension or hypertension
- Use of pressor medications for asymptomatic hypotension in the setting of routine spinal cord protection
- Atelectasis not requiring treatment
- Urinary retention or hematuria not requiring intervention other than urinary drainage
- Thrombocytopenia not requiring transfusion
- Mild leukocytosis not requiring treatment

The Investigator and/or IRB may require that these events are reported as adverse events. In this case, the Investigator will report these observations based on his medical judgment and requirements of the IRB.

A serious adverse event (SAE) is defined as one that suggests a significant hazard or side effect, regardless of the investigator's opinion on the relationship to the investigation. This includes, but may not be limited to, any event that:

- Is fatal
- Is life-threatening
- Requires or prolongs (>24 hours) inpatient hospitalization
- Is a persistent or significant disability or incapacity
- Is considered an important medical event

Important medical events may be considered serious by the investigator although they may not be immediately life threatening or result in death or prolong hospitalization. Such important medical events are those that may jeopardize the patient, require intervention to prevent one of the outcomes listed above, or result in urgent investigation. Examples include, but are not limited to, allergic bronchospasm, convulsions, and blood dyscrasias. SAEs will be recorded in the **Adverse Event CRF**. The investigator is also required to adhere to the reviewing IRB requirements for reporting of SAEs.

### **1.3 Protection against Study Risks**

**1.0 Informed Consent Process:** The consent process informs a volunteer about the study, indicates the participation is voluntary and he/she has the right to stop at any time. Risks are enumerated in the informed consent form and described orally during the consent process.

**2.0 Protection Against Risks:** Protection against risks includes a wide range of Study Group exclusion criteria, as well as rigorous post-treatment surveillance including follow-up visits at 30 days 6 and 12 months post-treatment, and annually for five years.

## **2.0 INTERIM ANALYSIS**

Interim analysis of the study is planned on an every six (6) month basis with the August Annual Progress Report serving as the starting point.

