### 8.9 Adverse Events

An adverse event is any new, undesirable medical occurrence or change (worsening) of a pre-existing condition that occurs in a patient, whether or not considered to be associated with the

product. Elective hospitalizations for pre-existing conditions are not adverse events. Requirements for reporting AEs are dependent upon the reviewing IRB policy. Adverse events will be reviewed by a Clinical Events Committee (CEC). The CEC will meet periodically, a minimum of annually. Adverse Event information is recorded in the **Adverse Event CRF**.

For purposes of this study, the following events are not considered adverse events, because they are expected to occur in conjunction with the index procedure or are associated with customary, standard care of patients undergoing endovascular TAAA repair procedures:

- Early post-operative pain (within 72 hours of index procedure) at the access site and/or related to position on procedure table (i.e. low back pain, abdominal pain, groin pain)
- Post-anesthesia/conscious sedation emesis, nausea, or headache (within 72 hours of index procedure)
- Electrolyte imbalance without clinical sequelae following index procedure, even if requiring correction
- Low grade temperature increase (< 100.5 °F)
- Blood loss not requiring transfusion
- Minor, localized tenderness, swelling, induration, bruising, erythema, hematoma etc. at vascular access site that does not require surgical intervention, evacuation, transfusion, or antibiotics
- Non-sustained arrhythmia not requiring treatment or intervention
- Prophylactic administration of atropine
- Prophylactic pacing
- Isolated, non-sustained PVCs/PACs
- Asymptomatic hypotension or hypertension
- Use of vaso-active medications for asymptomatic hypotension in the setting of routine spinal cord protection
- Atelectasis not requiring treatment
- Pleural effusion(s) not requiring treatment
- Urinary retention or hematuria not requiring intervention other than urinary drainage
- Thrombocytopenia not requiring transfusion
- Leukocytosis not requiring treatment
- Delirium, confusion or agitation within the first 72 hours postoperative unless such is found to be attributable to a TIA or Stroke or other new medical condition
- Constipation
- Chest pain that is determined to be non-cardiac in origin
- Peripheral edema not requiring treatment other than diuresis
- Shortness of breath not requiring treatment other than diuresis
- Bruising

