### **8.15 Deaths**

Any deaths that are device related must be reported to the FDA via an IDE supplement within 10 business days of knowledge of the event. Any deaths that are not device related are reported annually. The investigator is also required to adhere to the reviewing IRB requirements for reporting of deaths. In addition, patients with an implanted device who expire before completing the study should have the device explanted for evaluation by a pathologist if possible.

Aneurysm related death is defined as:

- any death occurring within 30 days of the B-TEVAR procedure, regardless of cause,
- death due to aneurysm rupture or
- within 30 days following any secondary procedure intended to treat the aneurysm.

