## **3.0 DATA AND SAFETY MONITORING**

The Principal Investigator (PI) will be responsible for ensuring participants' safety on a daily basis. The DSM will act in an advisory capacity to monitor participant safety, evaluate the progress of the study, and to review procedures for maintaining the confidentiality of data, the quality of data collection, management, and analyses. The PI and DSM will meet at least annually to review safety data.

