### **3.1 Frequency of Data and Safety Monitoring**

The DSM will be informed of serious adverse events that are device related and concern patient safety as soon as they occur. The PI will notify the FDA within 10 business days of knowledge of the SAE and the IRB per the reviewing IRB's requirements.

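### Immediate notice to the data safety monitor depends on attribution to the device, the primary safety endpoint does not, and the review that would catch the rest is guaranteed only once a year

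*Protocol*

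**What the plan says.** Three sets of provisions bear on this.

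**Cadence.** Appendix IX, 2.0 states: "Interim analysis of the study is planned on an every six (6) month basis". It names no recipient. Appendix IX, 3.0 then says: "The PI and DSM will meet at least annually to review safety data". Section 12.1 has: "The monitor will meet with the Clinical Events Committee annually, at a minimum". Section 12.2 has: "The CEC will provide their review to the DSM and will meet annually at a minimum". Section 8.9 repeats the same floor for the CEC, and section 9.2.1 describes the CEC's MAE review as annual. Appendix IX, 3.6 lists review of interim analyses among the DSM's duties, but only where appropriate and with no timetable.

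**Immediate notice.** Appendix IX, 3.1 states: "The DSM will be informed of serious adverse events that are device related and concern patient safety as soon as they occur". An event must therefore be serious, attributed to the device and relevant to patient safety. No other event has a stated prompt route to the DSM.

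**What the endpoint counts.** Sections 8.11 and 9.1.1 define the primary safety endpoint by a list of MAEs at 30 days and say that relation to the device is immaterial. Both classify every death in the first 30 days as TAAA related.

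**The concern.** The rule that decides what the DSM hears at once uses a criterion that the primary safety endpoint sets aside. Paralysis, renal failure, bowel ischaemia or death in this population can readily be put down to the procedure or to comorbidity. Each such event counts fully in the endpoint, yet none has to reach the DSM when it happens. The attribution that controls notice is also made when the event occurs, before the CEC has met to adjudicate it.

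The periodic reviews should be the backstop, but they are guaranteed only yearly, although interim output is planned twice as often. With recruitment expected to last under two years or about that long, a yearly floor leaves few guaranteed chances for an independent person to act on a cluster of such events while subjects are still being enrolled.

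**Working it through.** **Which events reach the DSM, and when**

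| Event within 30 days | In primary safety endpoint? | Immediate DSM notice required? | Latest guaranteed DSM or CEC look |
|---|---|---|---|
| Listed MAE that is serious, attributed to the device and bears on patient safety | Yes | Yes | At once |
| Death judged not device related | Yes | No | Next required meeting, up to 12 months |
| Paralysis judged procedural | Yes | No | Next required meeting, up to 12 months |
| Blood loss of 1,000 cc or more, judged procedural | Yes | No | Next required meeting, up to 12 months |

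**Inputs**

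- Sample size 60 (sections 5.0 and 5.2.1).
- 2-3 possibly eligible patients seen per month, and 18-24 months to recruit 60 (section 5.4).
- Interim every 6 months (Appendix IX, 2.0).
- Required meetings every 12 months (12.1, 12.2; Appendix IX, 3.0).

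**Step 1: the plan's own recruitment figure.** Months = 60 / monthly rate. At 3 a month, 60/3 = 20; at 2 a month, 60/2 = 30. That gives 20-30 months, so the stated 18-24 is not reproduced. Working backwards, 60/24 = 2.5 and 60/18 = 3.33 subjects a month. Section 5.4 allows that referrals may rise, which could explain the difference. Both rates are carried forward.

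**Step 2: subjects enrolled in a review gap.** Subjects = monthly rate x months.

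| Gap | From 18-24 month recruitment | From 2-3 a month, all enrolled |
|---|---|---|
| 12 months | 2.5 x 12 = 30 to 3.33 x 12 = 40 (50-67% of 60) | 2 x 12 = 24 to 3 x 12 = 36 (40-60%) |
| 6 months | 2.5 x 6 = 15 to 3.33 x 6 = 20 (25-33%) | 2 x 6 = 12 to 3 x 6 = 18 (20-30%) |

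**Step 3: reviews during recruitment.** Six-monthly interims: 18/6 = 3 to 24/6 = 4. Meetings guaranteed by an annual floor: 18/12 = 1.5, so at least one, to 24/12 = 2. About half the interims therefore have no required meeting attached.

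**Step 4: scale in deaths.** Section 2.1.4 cites 6% post-operative mortality for branched repair in high-risk patients. If that held here, a 12-month gap would contain 30 x 0.06 = 1.8 to 40 x 0.06 = 2.4 deaths, and a 6-month gap 0.9 to 1.2. At 24-36 subjects the 12-month figures are 1.4 to 2.2. The difference between the two cadences is about one expected death.

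**The case against.** The best reply is that nothing here conflicts. Every meeting clause but one is worded as a minimum, so six-monthly review is allowed; the exception, section 9.2.1, concerns the CEC's annual MAE review. The DSM is already tied to interim analyses in Appendix IX, 3.6. The CEC adjudicates all serious events whatever their relation to the device (12.2) and all deaths (9.2.1), and passes its review to the DSM. The investigator is responsible for safety daily, serious events go to the IRB under its rules, and unanticipated device effects go to the FDA and IRBs within 10 business days. For a single-centre feasibility study, annual meetings could be called a matter of preference.

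Much of this stands, and it rules out several stronger readings that a reader might infer:

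- **A contradiction between six-monthly interims and annual meetings.** A minimum does not forbid more frequent meetings.
- **No one would know for a year.** The investigator and the IRB would. What is missing is guaranteed DSM or CEC review.
- **Section 8.15 delays notice to the DSM.** Its sentence "Any deaths that are not device related are reported annually" follows one on reporting device-related deaths to the FDA. It sets no timing for the DSM.
- **Most subjects would be treated before any review.** The ranges run from 40% to 67%, depending on the accrual input, and do not establish that.
- **Deaths projected at 20%.** That is a population figure for open repair and is not an expectation for this procedure.

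What the reply does not answer is the notice rule. None of the other channels guarantees that a death or MAE judged unrelated to the device reaches the DSM or CEC within the year. The duty in Appendix IX, 3.6 is conditional and undated. A wider rule also carries a burden: one cited series had 41% major morbidity among its first 22 patients, and the MAE list includes blood loss alone, so immediate notice of every MAE could be frequent.

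**Conclusion.** The point holds as a gap in the monitoring rules. Immediate DSM notice is filtered by device attribution, the primary safety endpoint is not, and the periodic review that would pick up the remainder is guaranteed only once a year.

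The exposure between guaranteed reviews is about 30-40 of 60 subjects using the recruitment period, or 24-36 using the referral rate. These counts assume even accrual and meetings held no more often than required. The lower range also assumes that every possibly eligible patient enrols. They count enrolled subjects, some of whom may have only the first-stage TEVAR. In expected deaths the gain from six-monthly review is modest at the cited 6%. The stronger case is that the endpoint's own events should reach the person appointed to review them. This should be changed; the protocol can be run as written, but with a weaker safeguard than its planned interims allow.

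**What to change.** **Appendix IX, 3.1.** Require prompt notice to the DSM of every death within 30 days and every serious MAE, whatever its judged relation to the device. MAEs consisting only of blood loss can go in the six-monthly listing, which keeps the volume of single notices manageable.

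**Appendix IX, 2.0, 3.0 and 3.6.** State that each six-monthly interim goes to the DSM for review during enrolment, together with the MAEs that the CEC has adjudicated to date. Remove the conditional wording in 3.6 for that period. Annual meetings can remain the minimum once enrolment has ended.

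**Cost.** More notices to the DSM and about one extra review a year by existing members, using interim output that is already planned. No endpoint, sample size or treatment rule changes.
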